1.3.3 CONCLUSIONS

Considering the safety profile of the investigational medicinal products (IMPs), the minimal radiation risk to subjects, the measures in place to assure the subjects' safety and the expected scientific value, the overall risk/benefit assessment can be considered acceptable for the proposed study.

2. STUDY OBJECTIVES

2.1 PRIMARY OBJECTIVE

- To assess the effect of multiple doses of the HFA-152a propellant and the HFA-134a propellant (when administered not in combination with active compounds) on MCC.

Clinical Study Code No.: CLI-05993AB6-06

Version No.: 1.0

Date: 16 February 2023

EudraCT number: 2022-003247-97

2.2 SECONDARY OBJECTIVE

- To evaluate the general safety and tolerability of the two different propellants.

2.3 EXPLORATORY OBJECTIVE

[figure not shown]
Not applicable.

3. STUDY DESIGN

This is a Phase I, single-centre, multiple-dose, randomised, open-label, controlled, 2-way cross-over study to assess the effect on MCC of the new HFA-152a propellant (5 inhalations BID for 8 days) *versus* the marketed HFA-134a propellant (5 inhalations BID for 8 days) in adult (aged 18 to 55 years old [inclusive]) healthy volunteers.

The study design is shown in [Figure 1](#).

Figure 1. Study design

BID=Twice daily; D=Day; HFA=Hydrofluoroalkane; pMDI=Pressurised metered dose inhaler; V=Visit.

The study design proposed in the figure is just an example of one of the possible sequences.

[1] Randomisation performed at this visit.

[2] A follow-up visit (instead of a call) can be performed, if deemed necessary by the Investigator.

Study treatment

Approximately 20 subjects fulfilling the study eligibility criteria (see [Section 4.2](#) and [Section 4.3](#)) will be randomised to receive multiple doses (5 inhalations BID for 8 days) of each of the following treatments, according to an order determined by the randomisation list:

- HFA-152a propellant** (also referred to as “test treatment”): placebo HFA-152a propellant (not in combination with other active compounds) via pMDI;
- HFA-134a propellant** (also referred to as “reference treatment”): placebo HFA-134a propellant (not in combination with other active compounds) via pMDI.

Clinical Study Code No.: CLI-05993AB6-06

Version No.: 1.0

Date: 16 February 2023

EudraCT number: 2022-003247-97

Study visits

A total of 7 ambulatory study visits (Visit 1 [V1] to Visit 7 [V7]) and a follow-up call will be performed during the study, as follows:

- A **screening visit (V1)** will be carried-out 2 to 21 days before Treatment Period 1 (TP1), to assess a subject's eligibility.
- The **Investigational Phase** will comprise two 9-day treatment periods, separated by 7 to 14 days of wash-out from the propellant. Each treatment period will consist of 3 ambulatory visits at the investigational site.

Treatment Period 1 (TP1) will consist of:

- **Visit 2 (V2)** (Day -1 of TP1) including the baseline MCC assessments;
- **Visit 3 (V3)** (morning of Day 1 of TP1) including randomisation, the administration of the first dose of the assigned study treatment (HFA-152a or HFA-134a; according to each subject's randomisation arm), and the performance of the planned assessments;
Between V3 and V4, subjects will continue the study treatment administration at home, and will use daily record cards (DRCs) to record compliance to treatment.
- **Visit 4 (V4)** (morning of Day 8 of TP1) including the administration of the last dose of the study medication assigned during TP1, and the assessment of its effect by performing the planned assessments (including the post-treatment MCC assessments).

Treatment Period 2 (TP2) will consist of:

- **Visit 5 (V5)** (Day -1 of TP2) including a repetition of the baseline MCC assessments;
 - **Visit 6 (V6)** (morning of Day 1 of TP2) including the administration of the first dose of the other study treatment, and the performance of the planned assessments;
Between V6 and V7, subjects will continue the study treatment administration at home, and will use DRCs to record compliance to treatment.
 - **Visit 7 (V7)** (morning of Day 8 of TP2) including the administration of the last dose of the other study medication, and the assessment of its effect by performing the planned assessments (including the post-treatment MCC assessments).
- A **follow-up call** (or visit, if deemed necessary by the Investigator) will be performed between 7 and 10 days from the last intake of the study treatment (also in cases of premature discontinuation, if the early termination visit is performed less than 7 days after the last dose of the study treatment). A subject's participation in the study will end with the follow-up call (or visit, if deemed necessary by the Investigator).

The end of the study is defined as the last follow-up contact of the last subject in the study.

4. SUBJECT SELECTION CRITERIA

The Investigator will evaluate each subject on the selection criteria below and will make the final decision on eligibility.

Clinical Study Code No.: CLI-05993AB6-06

Version No.: 1.0

Date: 16 February 2023

EudraCT number: 2022-003247-97

4.1 SUBJECT RECRUITMENT

Male and female healthy volunteers aged 18 to 55 years old (inclusive) will be selected.

A total of 20 subjects will be randomised in accordance with the inclusion and exclusion criteria, in order to reach at least 18 evaluable subjects.

4.2 INCLUSION CRITERIA

Subjects must meet all of the following inclusion criteria to be eligible for enrolment into the study:

1. Subject's written informed consent obtained prior to any study-related procedure;
2. Healthy male and female subjects aged 18-55 years (inclusive);
3. Ability to understand the study procedures, the risks involved and ability to be trained to use the inhalers correctly;
4. Body Mass Index (BMI) between 18 and 30 kg/m² (extremes inclusive);
5. Non-smokers or ex-smokers who smoked < 5 pack-years (pack-years = the number of cigarette packs per day, times the number of years) and stopped smoking > 5 years prior to screening;
6. Good physical and mental status, determined on the basis of the medical history and a general clinical examination, at screening and before randomisation;
7. Vital signs within normal limits at screening: diastolic blood pressure (DBP) 40-89 mmHg, systolic blood pressure (SBP) 90-139 mmHg, extremes included (two measures performed after at least 5 minutes of resting, the mean value must be within the defined range); body temperature < 37.5°C;

Note: In case of abnormal vital signs at screening, the assessment can be repeated once before randomisation.

8. 12-lead digitised electrocardiogram (ECG) in triplicate considered as normal at screening:
40 ≤ heart rate (HR) ≤ 110 bpm, 120 ≤ PR interval (PR) ≤ 210 ms,
QRS interval (QRS) ≤ 120 ms, and QT interval corrected using Fridericia's formula (QTcF) ≤ 450 ms for males and QTcF ≤ 470 ms for females. The mean value must be within the defined range;

Note: In case of abnormal ECG at screening, the assessment can be repeated once before randomisation.

9. Lung function measurements within normal limits at screening: forced expiratory volume in 1 second (FEV₁)/forced vital capacity (FVC) > 0.70 and FEV₁ ≥ 80% predicted;

Note: In case of abnormal lung function at screening, the assessment can be repeated once before randomisation.

10. Female subjects fulfilling one of the following criteria:
 - a. Women of non-childbearing potential (WONCBP) defined as physiologically incapable of becoming pregnant (i.e. post-menopausal or permanently sterile, as per definitions given in [Appendix 2](#) and in Section 4.1 of the Clinical Trials Facilitation and Coordination Group guidance). Tubal ligation or partial surgical interventions are not acceptable. If indicated, as per Investigator's request, post-menopausal status may be confirmed by follicle-stimulating hormone (FSH) levels (according to local laboratory ranges);

Clinical Study Code No.: CLI-05993AB6-06

Version No.: 1.0

Date: 16 February 2023

EudraCT number: 2022-003247-97

- b. Women of childbearing potential (WOCBP) fulfilling one of the following criteria:
- WOCBP with fertile male partners: they and/or their partner must be willing to use a highly effective birth control method preferably with low user dependency, from the signature of the informed consent form (ICF) and until the follow-up call or;
 - WOCBP with non-fertile male partners (contraception is not required in this case).

Note: In case of hormonal contraception, an additional non-hormonal method (barrier method, preferably male condom) is required.

11. Male subjects fulfilling one of the following criteria:

- Fertile male subjects with a pregnant or non-pregnant WOCBP partner: they must be willing to use male condom, from the signature of the ICF until the follow-up call or;
- Non-fertile male subjects (contraception is not required in this case) or;
- Fertile male subjects with a WONCBP partner (contraception is not required in this case).

For the definition of WOCBP, fertile men and the list of highly effective birth control methods, refer to [Appendix 2](#) or to Section 4.1 of the Clinical Trials Facilitation and Coordination Group guidance.

Inclusion criterion #6 will be re-checked before randomisation.

4.3 EXCLUSION CRITERIA

The presence of any of the following will exclude a subject from study enrolment:

- Participation in another clinical study with an investigational drug in the 3 months or five half-lives of that investigational drug (whichever is longer) preceding the administration of the study treatment; a longer and more appropriate time could be considered by the Investigator based on the elimination half-life and/or long-term toxicity of the previous investigational drug;
- Clinically relevant and uncontrolled respiratory, cardiac, hepatic, gastrointestinal, renal, endocrine, metabolic, neurologic, or psychiatric disorders that may interfere with successful completion of the study (as described in this study protocol), according to the Investigator's judgment;
- Clinically relevant abnormal laboratory values at screening suggesting an unknown disease and requiring further clinical investigation, or which may impact the safety of the subject or the evaluation of the study results, according to the Investigator's judgment;

Note: In case of abnormal laboratory values that could indicate a temporary condition, the test can be performed again once before randomisation.

- Subjects with history of breathing problems (i.e. history of asthma including childhood asthma);
- Positive serology test for human immunodeficiency virus (HIV) 1 or HIV2 serology at screening;
- Positive results from the hepatitis serology, indicating acute or chronic hepatitis B or hepatitis C at screening (e.g. positive hepatitis B surface antigen [HBsAg], immunoglobulin M antibody to hepatitis B core [IgM anti-HBc] antigen, hepatitis C virus [HCV] antibody with detectable HCV ribonucleic acid [RNA]);
- Blood donation or blood loss (≥ 450 mL) during the 2 months prior to screening or randomisation;

Clinical Study Code No.: CLI-05993AB6-06

Version No.: 1.0

Date: 16 February 2023

EudraCT number: 2022-003247-97

8. Positive urine test for cotinine at screening or prior to randomisation;
Note: In case of a positive test, the test can be repeated once before randomisation.
9. Documented history of alcohol abuse within 12 months prior to screening, an average weekly alcohol intake of greater than 14 units, or a positive alcohol breath test at screening or prior to randomisation;
Note: In case of a positive test, the test can be repeated once before randomisation.
10. Documented history of drug abuse within 12 months prior to screening or a positive urine drug screen evaluated at screening or prior to randomisation;
Note: In case of a positive test, the test can be repeated once before randomisation.
11. Intake of non-permitted concomitant medications in the predefined period prior to screening or prior to randomisation, or subject expected to take non-permitted concomitant medications during the study;
12. Presence of any current infection, or previous infection that resolved less than 1 week prior to screening or to randomisation;
13. Known intolerance and/or hypersensitivity to any of the excipients contained in the formulation used in the study;
14. Documented coronavirus disease 2019 (COVID-19) diagnosis within the last 2 weeks, or associated complications/symptoms which have not resolved within 2 weeks prior to screening or prior to randomisation;
15. Heavy caffeine drinker (average of > 5 cups or glasses of caffeinated beverages [e.g. coffee, tea, cola], calculated by the number of standard espresso portions, per day);
16. For females only: pregnant or lactating women, where pregnancy is defined as the state of a female after conception and until termination of the gestation, confirmed by a positive serum human chorionic gonadotropin laboratory test;
Note: A serum pregnancy test will be performed at screening only. A urine pregnancy test will be collected on Day -1 of each treatment period.
17. The use of any kind of smoking electronic devices (e.g. e-cigarettes), within 6 months before screening or prior to randomisation;
18. Subjects for whom participation in this study will exceed a total radiation exposure of 5 mSv in the last 12-month period or 10 mSv in the last 5-year period;
19. Subjects with a total dosimetry value (including history of exposure through occupation) which, according to the Investigator's or a medically qualified designee's judgement, contraindicates their participation in the study.

The following criteria will be re-checked before randomisation: #7, #8, #9, #10, #11, #12, #14, #16 and #17.

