4.4 STUDY RESTRICTIONS

The following restrictions should be applied during the study and should be checked at the clinical unit at each visit, from the start of the screening visit and until the end of the last treatment period (i.e. when the subject leaves the clinic on Day 8 of TP2):

- No smoking or intake of substances containing nicotine, and no use of any kind of smoking electronic device (e.g. e cigarettes): during the entire study period (excluding the follow-up).

Clinical Study Code No.: CLI-05993AB6-06

Version No.: 1.0

Date: 16 February 2023

EudraCT number: 2022-003247-97

The following restriction should be applied before the screening visit:

- No strenuous activities: within 24 hours before the start of the screening visit and until the end of the visit.

The following restrictions should be applied prior to each visit with spirometry assessments (i.e. screening visit and Day 1 and Day 8 of both TP1 and TP2) and before each visit with MCC assessments (i.e. Day -1 and Day 8 of both TP1 and TP2):

- No intake of intoxicants such as alcohol, caffeine/xanthine containing beverages or food (coffee, tea, chocolate, cola) within 8 hours. Decaffeinated products are permitted;
- No strenuous activities within 1 hour;
- Avoiding wearing clothes that substantially restrict full chest and abdominal expansion.

The following restriction should be applied prior to each visit with blood collection for laboratory tests (i.e. the screening visit and Day 8 of TP2, or the early termination visit [if applicable]):

- No food intake: within 10 hours before the blood collection.

If these restrictions are not respected, the visit can be rescheduled once and all the information regarding the restriction(s) that are not respected will be recorded in the electronic case report form (eCRF). If the restriction(s) are again not respected at the rescheduled visit, the visit will be performed anyway and all the information regarding the restriction(s) that are not respected will be recorded in the eCRF.

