5. CONCOMITANT MEDICATIONS

5.1 PERMITTED CONCOMITANT MEDICATIONS

1. Occasional paracetamol (maximum 2 g per day, with a maximum of 10 g per 14 days, for mild non-excluding conditions [see exclusion criterion #2, [Section 4.3](#)]);
2. Hormonal contraceptives;
3. Hormonal replacement treatment for post-menopausal women;
4. COVID-19 vaccine during the wash-out periods and at least 7 days before Day 1 of each treatment period.

Note: Any systemic symptoms (e.g. myalgia, fever, chills, fatigue) after COVID-19 vaccine should subside 2 days before the next treatment period. Otherwise, wash-out period extension should be evaluated on a case-by-case basis.

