6.5 TREATMENT ALLOCATION

A balanced block randomisation list will be generated using a computerised system. Each subject will be assigned to one of the two possible sequences arranged in a 2x2 William design.

Each subject will be identified by a unique 4-digit code (SXXX) assigned at screening.

Clinical Study Code No.: CLI-05993AB6-06

Version No.: 1.0

Date: 16 February 2023

EudraCT number: 2022-003247-97

At randomisation (Day 1 of TP1), each eligible subject will be assigned the lowest randomisation number available (a unique 3-digits code [XXX]), according to a preestablished randomisation list:

- Subjects who do not meet the inclusion criteria and/or who meet the exclusion criteria at screening or prior to randomisation will not be eligible to enter the study. They will be considered as “screen failure subjects”;

Note: Screen failure subjects may be rescreened once. Rescreened subjects should be assigned a new participant number for the rescreening event.

- Subjects who fully meet the inclusion and exclusion criteria at screening or before randomisation will be eligible to enter the study;
- Subjects who prematurely terminate the study will be considered as “drop-out subjects”. These subjects cannot be screened again.

Note: If a subject is withdrawn or discontinued from the study after randomisation, the subject code and randomisation number will not be reassigned to another subject.

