7.1.2.2.1 DAY -1 OF TREATMENT PERIOD 2 (V5)

V5 is the first visit of TP2. It takes place after a 7- to 14-day wash-out period from the propellant administered during TP1.

The following procedures will take place at this ambulatory visit:

- **Study restrictions:** study restriction criteria and adherence to the wash-out requirements applicable before the MCC assessment will be checked, according to [Section 4.4](#);
- **Alcohol breath test:** will be performed using a specific kit;
- **Concomitant medications:** concomitant medications taken by the subject since the previous visit and during V5 will be checked and recorded;

Clinical Study Code No.: CLI-05993AB6-06

Version No.: 1.0

Date: 16 February 2023

EudraCT number: 2022-003247-97

- Urine test: urine samples will be collected for urine cotinine and drug panel test, according to [Section 7.2.6](#);
- Pregnancy test: urine samples will be collected from female subjects for pregnancy testing, according to [Section 7.2.6](#);
- Body temperature: will be assessed according to [Section 7.2.3](#);
- AE recording: the status of AEs ongoing at V4 will be checked and updated in the eCRF when applicable. Any new AE occurring since the previous visit will be checked and recorded in the eCRF, as well as the related concomitant medications. Any AE occurring during the study visit must also be monitored and recorded in the eCRF;
- MCC assessment: subjects will be administered a radiotracer. Image acquisitions for the assessment of MCC will be performed at 0 (immediately), 15 minutes, 30 minutes, 1 hour, 1 hour 30 minutes, 2 hours, 2 hours 30 minutes, 3 hours and 4 hours after the administration of a radiotracer, according to [Section 7.2.1](#).

Before discharge, subjects will be given the following instructions:

- To adhere to the study restrictions and to the pre-spirometry wash-out requirements before coming to V6, according to [Section 4.4](#);
- To avoid taking any of the non-permitted concomitant medications, according to [Section 5.2](#).

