### 2.1.3 *Inferential statistics*

All statistical comparisons will be made using two-sided tests at the 0.05 significance level unless specifically stated otherwise.

The change from baseline in  $PPR_2$  and  $PPR_4$  at Day 8 will be analysed using an analysis of covariance (ANCOVA) model, including treatment, subject and period as fixed effects, and  $PPR_2$  (or  $PPR_4$ ) at baseline (i.e., Day -1) as a covariate. The adjusted mean change from baseline obtained with each treatment and the adjusted mean difference between HFA-152a and HFA-134a with their 95% confidence intervals (CIs) and p-values will be estimated by the model.

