## 5. GENERAL METHODOLOGY

### 5.1 ANALYSIS SETS

#### 5.1.1 *Analysis sets*

The following analysis sets will be considered in the statistical analysis:

Randomised Set (RND):	subjects who were randomised into this study
Safety Set (SAF):	subjects who were randomised and received at least one dose of study treatment (analysed as treated)
Intent-to-Treat (ITT) Analysis Set:	subjects who were randomised and received at least one dose of study treatment (analysed as randomised)
Per Protocol (PP) Analysis Set:	subjects from the ITT, excluding the subjects with any important protocol deviations leading to data exclusion

Notes:

- Randomised is defined as having a randomisation date in the database or any information to confirm randomisation.
- Having received at least one dose of study treatment is defined as having an exposure date or any information confirming exposure.
- Exact definition of important protocol deviations impacting the analysis sets (e.g. wrong inclusions, poor compliance, non-permitted medications) will be discussed by the study team during the review of the data and described in the Data Review Report.

Unless stated otherwise, the ITT will be used for the general characteristics and SAF for safety tables and the RND will be used for listings. ITT and PP Analysis Set will be used for the study variables tables and figures.

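### Should the plan re-check the infection criteria before Period 2, or fix a data rule for an infection at a later MCC scan?

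*Protocol*

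**What the plan says.** Criterion #12 in Protocol section 4.3 reads "Presence of any current infection, or previous infection that resolved less than 1 week prior to screening or to randomisation". Criterion #14 (COVID-19) is tied to the same two moments. Both are on the list to be repeated: "The following criteria will be re-checked before randomisation: #7, #8, #9, #10, #11, #12, #14, #16 and #17". Section 6.5 fixes when that is: "At randomisation (Day 1 of TP1), each eligible subject will be assigned the lowest randomisation number available". Table 2 marks eligibility checks at V1, V2 and V3, the last two in Period 1 only.

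Other disturbances do have a stated route. For caffeine, alcohol, exertion and similar restrictions, section 4.4 says "If these restrictions are not respected, the visit can be rescheduled once"; if the restriction is broken again, the visit goes ahead and the breach is recorded. For symptoms after a COVID-19 vaccine, section 5.1 says "Otherwise, wash-out period extension should be evaluated on a case-by-case basis".

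At V5 the protocol requires temperature, concomitant medications and adverse events to be checked, including that "the status of AEs ongoing at V4 will be checked and updated in the eCRF when applicable". On the data side, SAP section 5.1.1 states: "Exact definition of important protocol deviations impacting the analysis sets (e.g. wrong inclusions, poor compliance, non-permitted medications) will be discussed by the study team". SAP sections 5.1.3, 5.2.2 and 5.3.4 leave exclusion of values, a different baseline and outliers to the data review, with decisions documented.

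**The concern.** The protocol treats infection as a reason not to enter the trial, and its rationale (section 1.2) says that lung disease affects MCC. Yet a subject who falls ill after randomisation can have the Period 2 baseline scan or either Day 8 scan while infected, and no consequence is written down. Caffeine has a rescheduling route and infection has none.

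The trial is also small and open-label. A single disturbed scan could carry weight in the PPR2 or PPR4 comparison, and the choice to keep or drop it would be made at a data review where treatment is known. If that choice were steered by the result, the primary comparison would be less trustworthy.

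**Working it through.** **Is the gap in the text?** Yes. From randomisation (V3) to V7 is 7 + (7 to 14) + 1 + 7 = 22 to 29 days with no repeat of #12 or #14. The procedure lists for V4, V5 and V7 contain no infection check.

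**What happens if the plan is followed as written?**
- The illness is seen. Adverse events, medications and body temperature are recorded at V4, V5 and V7; the daily record card covers the days at home; section 7.1 requires monitoring for COVID-19 symptoms.
- An infection treated with anything outside the permitted list (section 5.2) is a non-permitted medication, which is a listed important deviation (section 12.3.1) and a named example for per-protocol exclusion (section 12.2).
- An infection judged to make continuing unsafe leads to discontinuation (section 4.5).
- An infection that is untreated, or treated only with permitted paracetamol, matches none of the deviation examples. Unless the data review decides otherwise, its MCC values stay in.

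**How often?** The documents give no rate. Assume 1 to 3 infections per person-year, each lasting 7 days. The chance of being ill on a given scan day is 1 − exp(−rate × 7/365), which is 1.9% to 5.6%. Over 40 Day 8 scans that is 0.8 to 2.2 affected scans; over 20 V5 scans, 0.4 to 1.1.

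**How large?** The documents give no SD and no infection effect. Take 18 subjects, 9 per sequence, and the planned model, "including treatment, subject and period as fixed effects", plus the Day -1 value. Let σ be its residual SD and X the disturbance at one Day 8 scan.
- Shift in the treatment difference: X/18. X = 20 gives 1.11 points; X = 10 gives 0.56.
- Undisturbed standard error: σ√(2/18). For σ = 5 this is 1.67. Residual df are 36 − 1 − 17 − 1 − 1 − 1 = 15, t = 2.131, so the 95% half-width is 3.55. The 20-point case is therefore a shift of 1.11/1.67 = 0.67 SE, and the 10-point case 0.33 SE.
- Inflation of the SE, ignoring the covariate's one df: √{1 + X²(8/9)/16 ÷ 2σ²}.

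| σ | X = 10 | X = 20 |
|---|---|---|
| 3.5 | +11% | +38% |
| 4.3 | +7% | +27% |
| 5 | +5% | +20% |
| 10 | +1% | +5% |

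Simulation of the full model, covariate included, agrees with these values.

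- V5 disturbed alone, X = 20, σ = 5: simulated shift 0 to 0.4 points and SE +0 to 4%, as the share of visit-to-visit variance common to a period goes from 0 to 0.5. The Day -1 covariate absorbs most of it.
- Two 20-point Day 8 disturbances on the same treatment add to 2 × 1.11 = 2.2 points, still inside the half-width; one on each treatment cancel.

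**Would repeating the criteria at V5 help?** Their look-back windows refer to screening or randomisation, so they could not be applied at V5 as worded. A check there would cover the scan where a disturbance matters least and would not reach either Day 8 scan.

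**The case for a change.** The best case for a change is about discretion, not noise. The data review may exclude values, replace a baseline or drop outliers, with no infection criterion and with treatment known. One SAP sentence before that review would close this off at almost no cost: ITT unchanged, affected scans listed, one supportive analysis without the affected periods.

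Part of this stands. The discretion exists, and a Day 8 disturbance is not absorbed by the covariate. But the first element of that sentence is already the default, since nothing in the plan removes an infected subject's data from ITT. Adverse events and all MCC values are listed by subject, so a reader can find the scans concerned. SAP section 5.1.3 ties time-point exclusion to important protocol deviations; those are finalised before database lock, and ITT and per-protocol results are both shown. What remains is an optional supportive table, and it costs precision. Leaving out one subject raises the SE by √(18/17) − 1 = 2.9%; leaving out three raises it by √(18/15) − 1 = 9.5%.

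The different treatment of caffeine, vaccine symptoms and infection is not a contradiction. Sections 4.3, 4.4 and 5.1 cover entry, subject behaviour and vaccination respectively, and section 7.1.2.2.1 lists the V5 procedures.

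**Conclusion.** No change is needed. The absence of an infection rule after randomisation is real, but it is a detail that the study team can handle sensibly with what the plan already provides: recorded adverse events, an ITT analysis that keeps the data, a parallel per-protocol analysis and documented exclusions. Because sequence is randomised, infections add noise and chance imbalance; they do not favour either propellant.

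Under the assumptions used (18 subjects, residual SD 5, one Day 8 scan off by 20 points) the result moves by about 1.1 points, roughly two-thirds of a standard error, and the SE rises by about 20%. A larger SD or a smaller disturbance lowers the SE rise to 5% or less. A smaller SD raises it: 38% at 3.5. All these inputs are assumptions, since the documents give none. The study has no formal sample size and no equivalence margin, so no pre-set decision turns on a shift of this size.
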